6.4 Safety

Safety variables are:

- Adverse events
- Mortality
- Laboratory parameters
- Vital signs
- ECG parameters
- Blood gas analysis

Baseline for continuous safety variables will be week 0 of study 12934.

The incidence of treatment-emergent adverse events during the extension will be tabulated by treatment group. Adverse events are considered to be treatment-emergent if they have started or worsened after first application of study medication up to 2 days after end of treatment with study medication. Further tables will be produced for serious and/or drug-related treatment-emergent adverse events. The incidence of adverse events during follow-up (that is, adverse events occurring more than 2 days after end of treatment with study medication) will be

tabulated separately. The incidence of adverse events that started in the main study 12934 and continue into study 12935 will also be tabulated separately.

In addition, given the varying length of time subjects are in the long-term study, the incidence of treatment-emergent adverse events will also be give per 100 subject years.

Mortality will be summarized descriptively. Any deaths in the study period will be listed, with day of death relative to start and stop of study drug and cause of death.

The safety evaluation of laboratory data will include

- listings of laboratory data out of normal range
- incidence rates of treatment-emergent laboratory values outside of normal range by treatment group
- incidence rates of pre-specified laboratory data abnormalities by treatment group
- descriptive analysis of continuous laboratory parameters, and their changes from baseline by visit and treatment group

The specific laboratory data abnormalities are consistent with those requested by the Data Monitoring Committee or as part of the company medical safety review, and include hepatic transaminases, bilirubin and creatinine (and calculated eGFR).

With global amendment 11, a laboratory value testing was completely removed from the study protocol.

Vital signs (systolic BP, diastolic BP, heart rate and weight) and blood gas analysis will be summarised by visit and treatment group for the population of subjects valid for safety.

For ECGs, the status pre-treatment and post treatment-initiation will be tabulated. The incidence rates of treatment-emergent ECG abnormalities will be tabulated by treatment group. A descriptive analysis of continuous ECG parameters and their changes from baseline by visit and treatment group will also be presented.

7. Document history and changes in the planned statistical analysis

SAP version 2.0 dated 30 Sep 2009

SAP version 3.0 dated 15 Mar 2012

SAP version 4.0 dated 29 May 2012

SAP version 5.0 dated 25 Jul 2019, Update to new template

8. References

Not applicable.

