#### Titration Phase (8 weeks):

##### General aspects:

During the first eight weeks of the trial, patients from the Placebo Arm and from the BAY 63-2521 1.5 mg Dose Arm (applies only to patients who reached the 1.5 mg tid level) of PATENT-1 trial will be up-titrated, if tolerated, up to 2.5 mg BAY 63-2521 tid according to an individual dose titration scheme.

To maintain the blinding of PATENT-1, the PATENT-2 study medication (BAY 63-2521) is blinded with respect to the dose during the Titration Phase and investigators will not know at which dose level a certain patient enters the PATENT-2 trial.

Patients from the BAY 63-2521 Individual Dose Titration Arm and the BAY 63-2521 1.5 mg Dose Arm will enter the extension trial on the same dose level

which they have received on the last day of PATENT-1, while patients from the Placebo Arm will start at Visit 1 with a BAY 63-2521 dose of 1.0 mg tid.

To allow a blinded individual dose titration, the titration will be performed with the aid of an IVR-System. At each Titration Visit (with the exception of Visit 1) the investigator needs to decide, based on the patient's systolic blood pressure, if the study medication dose should be modified. The respective decision (increase, maintain or decrease dose) must be entered in the IVR-System that will automatically allocate the right dose in accordance with the respective titration scheme. Afterwards, the investigator will be informed by the system, which of the blinded medication bottles (blinded with respect to the dose) needs to be handed over for the next titration period (starts always with the morning dose).

Independently from the patient's allocation to a specific treatment arm in PATENT-1, the investigators will apply the following blood pressure based titration rules for their dose decision in PATENT-2:

The individual study medication dose of the next titration step will be determined every 2 weeks according to the peripheral SBP measured at trough before intake of the morning dose under consideration of the following algorithm (= individual dose titration scheme):

- If trough SBP  $\geq 95$  mmHg, increase dose (+0.5 mg tid).
- If trough SBP 90 - 94 mmHg, maintain dose.
- If trough SBP  $< 90$  mmHg without symptoms of hypotension, reduce dose (-0.5 mg tid).
- If any SBP  $< 90$  mmHg with clinical symptoms of hypotension such as dizziness or presyncope, stop study treatment; restart after 24 hours with reduced dose (-0.5 mg tid).

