## **4.2 Selection of Study Population**

### **4.2.1 Inclusion Criteria**

- Patients who have completed 12 weeks of treatment in the double blind trial PATENT-1.
- Patients must have given their written informed consent to participate in the study after having received adequate previous information and prior to any study-specific procedures.

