#### 4.6.3 Assessment Periods

##### Visit 1 at Day 0

Patients who finalized at Visit 6 the PATENT-1 trial and underwent invasive hemodynamic measurements may remain in the clinic until the next day (optional hospital stay).

At the day after finalization of PATENT-1 trial (= Visit 1 of PATENT -2), patients who fulfill the in/exclusion criteria and signed the informed consent form will be included into PATENT -2.

**Please Note:** it is not permitted to include a patient into the extension study on the same day of V6 of PATENT -1 (applies even if Visit 6 investigations were performed at two consecutive days).

On Visit 1 prior to first administration of PATENT-2 study medication, blood pressure and heart rate will be measured.

Subsequently, the patients will be allocated via the IVR-System to their individual BAY 63-2521 starting dose. In this context, the IVR-System will consider the patient's treatment arm allocation from the PATENT-1 trial (for further details refer to Section 4.1).

Two to three hours after the first intake of study medication, blood pressure and heart rate measurement will be repeated (for further details about the order of the procedures and the temporal relationship refer to Section 10.1).

Between six to eight hours after first study medication intake, the patients should take the second dose of study medication (second measurement cycle). One to zero hours before intake of second dose of study medication, blood pressure and heart rate will be measured, pharmacokinetic blood samples will be collected and a 12-lead electrocardiogram will be recorded. 2-3 hours after intake of second dose of study medication the blood pressure and heart rate should be measured (for further details about the order of the procedures and the temporal relationship refer to Section 10.1).

In addition to the measurements related to the measurement cycles, Adverse Events will be questioned and documented. Adverse events that occur before intake of first dose of PATENT-2 medication will be allocated to PATENT-1.

The study medication should be taken six to eight hours apart. If during the profile visit the systolic blood pressure falls below 90 mmHg with clinical symptoms of hypotension such as dizziness or presyncope, the study medication should be reduced by 0.5 mg tid or if deemed necessary interrupted (see section 4.1).

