### **Laboratory Parameters**

All blood samples will be analyzed in a central laboratory until V6.

Laboratory procedures will be described in a separate laboratory manual.

At the latest at the end of the study when all planned analyses are completed, all blood samples will be destroyed.

- ***Hematology, clinical chemistry, coagulation test***

Hematology (white blood cell differential count, erythrocytes, hemoglobin, hematocrit, platelets)

Coagulation tests (PTT, INR)

Clinical chemistry (AST, ALT, ALP, GGT, GLDH, CK, lipase, CHE, creatinine, urea, uric acid, total bilirubin, total protein, serum albumin, sodium, potassium, calcium, phosphate)

Note: Calcium and phosphate will only be analyzed for patients who were included under amendment 8 of study 12934.

Frequency: At every visit until V6 (except Visit 1)

- ***NT-proBNP***

Frequency: At every visit until V6 with the exception of Visit 1 and Safety Follow Up Visit

Changes from baseline NT-proBNP will be considered as a secondary efficacy endpoint in PATENT-1. To ensure the blinding of the treatment regime of PATENT-1, the results of the NT-pro BNP determinations at PATENT -2 Visits 2-5 will not be forwarded to the investigators before lock of the PATENT-1 database. In contrast to that the results of the NT-pro BNP determination at PATENT-2, Visit 6 will be forwarded to the investigators.

- ***Pregnancy testing***

Methodology: Determination of  $\beta$ - human chorionic gonadotropin in blood serum or urine

Frequency: Will be performed centrally at Visit 6 and locally at least at every Main-Study Phase Visit (V7-Vn) and at Safety Follow Up Visit. Based on country specific regulations further measurements might be performed.

In addition to the above mentioned serum  $\beta$ - human chorionic gonadotropin tests, a urine test will be performed at Visit 6 of PATENT-1 study if the patient will

participate in the extension study. Female patients with childbearing potential can be enrolled into the extension study based on the result of this test.

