## **6. STATISTICAL METHODS AND DETERMINATION OF SAMPLE SIZE**

### **6.1 Statistical and Analytical Plans**

The aim of this long-term extension study is primarily the assessment of safety and tolerability, so no single primary variable has been identified. Patient numbers will be determined by those completing the PATENT-1 study and willing to enter the PATENT-2 study. As the extension is of an open label design with no comparator group, all statistical analyses will be descriptive. The summary tables will be presented for the overall group of patients, and also split by previous treatment groups in PATENT-1. Baseline will be week 0 in PATENT-1 (changed with amendment 11).

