5.1 Assignment of analysis sets

A subject is valid for the long-term safety and efficacy analysis, if at least one dose of study medication in the extension period was administered.

6. Statistical Methodology

The statistical evaluation will be performed according to the company Global Standards for demography and safety analyses when these have been published (see section 1 for table templates), the statistical methods given in the protocol and, if applicable, any relevant protocol amendments.

For all descriptive analyses, unless otherwise specified, it is planned to summarize the group of subjects as a whole ("all subjects") and by the following groups:

Reference Number: RD-OI-0119

Supplement Version: 8

- Patients randomized to riociguat individual titration in the main phase who stayed on riociguat in the LTE phase, referred to as "riociguat individual titration"
- Patients randomized to placebo in the main phase who switched to riociguat in the LTE phase, referred to as "placebo-riociguat"

By week 8 of the extension, all subjects should be receiving riociguat at the optimized dose, but prior to this there may be some differences between the treatment groups as those subjects in the placebo group will be receiving active medication for the first time, or those in the 1.5 mg group will be up-titrated above 1.5 mg for the first time.

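### Continuous safety variables in the placebo-riociguat group are measured only from PATENT-1 week 0, with no reference value from just before the first riociguat dose

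*SAP*

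**What the plan says.** SAP 6.4 fixes one reference for all former treatment groups: "Baseline for continuous safety variables will be week 0 of study 12934". Protocol 6.1 does the same and marks the text as changed with amendment 11, so the two documents agree.

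SAP 6.4 plans changes from baseline by visit and treatment group for laboratory and ECG parameters. Protocol 6.1 adds changes from baseline for vital signs. SAP 6.4 also summarises blood gas values by visit and group, and as a continuous safety variable these fall under the same baseline rule.

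SAP section 6 displays former placebo patients as a group of their own: "Patients randomized to placebo in the main phase who switched to riociguat in the LTE phase". It acknowledges that early in the extension "those subjects in the placebo group will be receiving active medication for the first time". Under Protocol 4.1, "patients from the Placebo Arm will start at Visit 1 with a BAY 63-2521 dose of 1.0 mg tid".

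On the values available before that dose, Protocol 4.6.3 says: "On Visit 1 prior to first administration of PATENT-2 study medication, blood pressure and heart rate will be measured". The flow chart in Protocol 10.1 places blood pressure, heart rate, weight, ECG, laboratory sampling and blood gas analysis at PATENT-1 Visit 6, one day earlier. Neither document makes any of these a reference value.

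**The concern.** For patients who took riociguat in PATENT-1, week 0 precedes any riociguat, and everything after it is time on drug. For the placebo-riociguat group, week 0 lies 12 weeks before the first riociguat dose. A change from week 0 in this group therefore mixes two periods, and the tables offer no way to separate them within patients.

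This matters because the study objective is long-term safety and tolerability, and descriptive change tables are the main planned summary of how these continuous measures move. The former placebo patients are the only ones whose first exposure to riociguat falls inside the extension. A shift in blood pressure, heart rate, ECG or laboratory values at first exposure could look smaller or larger than it was, depending on what happened over the preceding 12 weeks.

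**Working it through.** **Inputs.**
- Baseline for continuous safety variables: PATENT-1 week 0 (SAP 6.4, Protocol 6.1).
- Time from that baseline to entry: nominally 12 weeks. Protocol 4.2.1 admits "Patients who have completed 12 weeks of treatment in the double blind trial PATENT-1".
- First riociguat dose in former placebo patients: PATENT-2 Visit 1, day 0 (Protocol 4.1).
- Visit days: V2 = 14, V3 = 28, V4 = 42, V5 = 56, V6 = 84, V7 = 174 (Protocol 10.1).
- Mean change over the 12 placebo weeks: not given in either document.

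The plan has no figure of its own to reproduce. Its analyses are descriptive, and Protocol 6.2 gives no sample size.

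**Step 1: decomposition.** For a former placebo patient with value Y,

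Y(visit) − Y(week 0) = [Y(visit) − Y(last before riociguat)] + [Y(last before riociguat) − Y(week 0)].

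The second bracket, d, is the change over the placebo period. This is an identity and needs no assumption. In a fixed set of patients, the mean of d enters the mean change equally at every visit.

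**Step 2: share of the interval spent on placebo**, 12 / (12 + visit day / 7).

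| Visit | Weeks on riociguat | Weeks since week 0 | Placebo share |
|---|---|---|---|
| V2 | 2.0 | 14.0 | 85.7% |
| V3 | 4.0 | 16.0 | 75.0% |
| V4 | 6.0 | 18.0 | 66.7% |
| V5 | 8.0 | 20.0 | 60.0% |
| V6 | 12.0 | 24.0 | 50.0% |
| V7 | 24.9 | 36.9 | 32.6% |

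In the current flow chart, ECG and laboratory sampling stop at V6, and V6 is the only on-treatment blood gas assessment in PATENT-2. So at every visit scheduled there for these measures, at least half of the interval precedes any riociguat. Any later values collected under superseded schedules would have a smaller share. These are shares of time, not of the size of the change.

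**Step 3: effect on the mean (assumed values).** Suppose the mean change since the last pre-riociguat value is −5 units and d is anywhere from −5 to +5. The tabulated change is −5 + d:

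| d | −5 | −2 | 0 | +2 | +5 |
|---|---|---|---|---|---|
| Reported change | −10 | −7 | −5 | −3 | 0 |

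The range is illustrative only. The documents support neither a value nor a sign for d.

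**Step 4: which pre-riociguat values exist.**
- Blood pressure and heart rate: measured before the first dose at Visit 1.
- ECG: the Visit 1 recording is made shortly before the second dose, so after the first. The last pre-riociguat recording is at PATENT-1 Visit 6.
- Laboratory, blood gas and weight: not scheduled at Visit 1. The last pre-riociguat value is at PATENT-1 Visit 6.

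Visit 1 alone therefore cannot serve as the reference for every variable.

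**Step 5: can the tables be worked backwards?** The mean of d could be approximated by subtracting visit means if the Visit 1 or PATENT-1 Visit 6 values were displayed, to which the SAP does not explicitly commit, and if the same patients contributed. The standard deviation, median, minimum and maximum of the within-patient change, which Protocol 6.1 calls for, cannot be recovered from visit summaries.

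**The case against.** The strongest reply is that week 0 is a deliberate choice, consistent across both documents. It gives both displayed groups the same formal definition: the same starting point, before any trial treatment, with the same elapsed time at each visit. The analysis is descriptive and has no comparator. The former placebo patients appear under their own label, and SAP section 6 warns that groups may differ before week 8. All of this stands, and it is why the point concerns a missing supplement and not a contradiction.

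A reader might infer that the plan attributes placebo-period change to riociguat. It does not: no passage draws a causal conclusion from change since week 0. The risk lies in how a table is read.

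A reader might also extend the point to the whole safety analysis. The documents do not support that. Treatment-emergent adverse events are tabulated for the extension and tied to the start of study medication. Events before the first PATENT-2 dose belong to PATENT-1, and those continuing from the main study are tabulated separately. Nor does recognition of hypotension depend on mean change: titration uses absolute systolic pressure, Visit 1 includes repeat readings after each dose, and every syncope is reported as a serious adverse event.

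For blood pressure and heart rate, a Visit 1 row in the by-visit summaries would let a reader judge the placebo-period change roughly. This weakens any claim that a fall would be hidden, but it leaves the within-patient distribution unavailable.

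Finally, a change from the last pre-riociguat value is no clean drug effect. In an uncontrolled phase it still mixes drug, time and regression to the mean, and Visit 1 follows the day after PATENT-1 ends, possibly after invasive measurements. The placebo-controlled comparison belongs to PATENT-1. This objection stands and determines how the added table must be labelled.

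**Conclusion.** The point holds for changes from baseline in continuous safety variables in the placebo-riociguat group. As planned, they combine 12 weeks on placebo with time on riociguat, and no pre-riociguat reference is defined. The placebo share of the interval falls from 85.7% at V2 to 50.0% at V6, assuming nominal visit timing and exactly 12 weeks in PATENT-1. The mean is shifted by the mean 12-week placebo change, whose size and direction are unknown. It could be negligible, so material bias is not shown. This is an inexpensive improvement to the SAP, and the week 0 baseline is not an error.

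**What to change.** Keep PATENT-1 week 0 as the baseline for the common tables. In SAP 6.4, add for the placebo-riociguat group only a descriptive summary of change from the last value before the first riociguat dose, using:

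- the Visit 1 pre-dose measurement for blood pressure and heart rate;
- PATENT-1 Visit 6 for ECG, laboratory, blood gas and weight.

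Title these tables as uncontrolled pre-post changes, and state the reference visit and the time since first riociguat dose in each.

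The cost is about one further table per safety domain for one group. The values are already scheduled, so no new assessment is needed. The drawback is a second reference point. Intervals in the added tables run 2, 8 and 12 weeks at V2, V5 and V6, against 14, 20 and 24 weeks in the week 0 tables, so the two sets must not be read side by side as like for like.

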### **Blood gas analysis**

SaO2(%)

PaO2(mmHg)

PaCO2(mmHg)

**Supplemental oxygen** “yes” or “no” (If the patient receives supplemental oxygen the amount will be recorded in the electronic CRF in liter per minute)

Methodology: Capillary or arterial blood gas analysis

Frequency: At V6

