### **Other Events of Special Interest**

The first occurrence of the following event of special interest needs to be documented in the electronic CRF, but will not be considered for the calculation of the combined end point “Time To Clinical Worsening”:

- Initiation of a supplemental long-term oxygen therapy (= oxygen application for more than 30 days at a stretch) or persistent modification of a pre-existing supplemental long term oxygen therapy (ie need for a persistent increase of the amount of delivered oxygen for more than 30 days) due to worsening pulmonary hypertension.b

aTransient deteriorations of clinical status requiring hospitalization, treatable by eg short time application of iv diuretics, positive inotropic agents or non-invasive ventilation and allowing patients discharge within 48 hours are not considered as persistent with respect to the event of special interest definition.

bIn case of clinical deterioration the investigator has to assess carefully if the deterioration of the patient’s condition (eg worsening functional class) is related to the underlying pulmonary hypertension or can be explained by an alternative cause (eg transient infection, musculoskeletal disease, surgical or medical intervention other than PH related, exacerbation of a concomitant lung disease, lacking compliance of medication intake). Only persistent clinical deteriorations caused by the underlying pulmonary hypertension will be considered as events of special interest.

Frequency: At every visit with the exception of Visit 1 and Safety Follow-Up Visit the investigator must check if an event of special interest has occurred in the period between start and termination of the study drug treatment. With respect to each subcategory (eg “hospitalization due to persistent worsening of pulmonary

hypertension”) it is only necessary to document the first occurrence of such an event in the electronic CRF.

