## **10.3 Blood Gas Analysis**

Blood gases are to be obtained from the arterial blood or from arterialized capillary blood. All samples should be obtained with the patient resting in a sitting or supine position for at least 10 min. If

possible no supplementary oxygen should be given during the resting period and while blood samples are drawn. If the patient requires oxygen, care should be taken that all samples are drawn with the same flow of oxygen throughout the study whenever possible. Printouts from the analyzer have to be stored in the patient file and the measured values have to be transferred into the electronic CRF.

Blood gas measurement
Actual time
Date
SaO 2 (%)
PaO 2 (mmHg)
PaCO 2 (mmHg)
Supplemental oxygen "Yes" or "No"
If "Yes", amount of supplemental O 2 (l/min)

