4.1 General Principles

The statistical evaluation will be performed by using the software package SAS release 9.2 or higher (SAS Institute Inc., Cary, NC, USA). All variables will be analyzed by descriptive statistical methods. The number of data available and missing data, mean, standard deviation, minimum, quartiles, median, and maximum will be calculated for metric data. Frequency tables will be generated for categorical data.

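### SAP 6.4 summarises blood gases without the oxygen status recorded at each sample, so a patient sampled on newly started oxygen can mask worsening in the safety table

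*SAP*

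**What the plan says.** Protocol 4.6.1 lists blood gas among the safety variables. Protocol 4.6.4 defines it as SaO2, PaO2 and PaCO2, and in the current text schedules it in the extension at Visit 6 only (day 84, week 12). Protocol 4.6.4 and 10.3 both have supplemental oxygen recorded with the measurement, as yes or no and, if yes, in litres per minute.

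Protocol 10.3 sets two rules for sampling. The first is that, where possible, the patient receives no supplementary oxygen during the rest before the sample or while it is taken. The second covers patients who need oxygen: "care should be taken that all samples are drawn with the same flow of oxygen throughout the study whenever possible".

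The protocol expects oxygen use to change in some patients. "Initiation of a supplemental long-term oxygen therapy", or a lasting increase in an existing one, because of worsening pulmonary hypertension is documented as an event of special interest. It is kept outside the Time To Clinical Worsening composite.

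The SAP's analysis of the variable is one clause in 6.4: "blood gas analysis will be summarised by visit and treatment group", in the safety population. The same section states: "Baseline for continuous safety variables will be week 0 of study 12934". SAP 4.1 adds: "All variables will be analyzed by descriptive statistical methods". The SAP text contains no split, restriction or adjustment of the blood gas summary by oxygen status or flow.

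**The concern.** PaO2 and SaO2 cannot be interpreted without knowing whether the patient was breathing supplemental oxygen. The plan collects that information and then leaves it out of the one analysis that needs it.

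The resulting error is not neutral. A patient whose oxygenation falls far enough to need oxygen, and who is then sampled on it, enters the Visit 6 summary with a value higher than the lungs alone would give. The patients who worsened therefore push the group mean upward, and the table can show stability or improvement where there was decline. With one scheduled extension measurement in the current text, no later scheduled value would correct a misleading Visit 6 figure.

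At stake is how one descriptive safety table is read. No test, decision rule or primary result depends on it.

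**Working it through.** **Is there a figure to reproduce?** No. Protocol 6.2 gives no sample size, all analyses are descriptive, and the documents state no rate of oxygen start, no expected blood gas change and no standard deviation. The check is a comparison of the texts followed by an illustration on assumed values.

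**Step 1: can the sampling rules remove the problem?**
- The off-oxygen rule applies only where possible. It fails for a patient who cannot be taken off oxygen.
- The constant-flow rule is also qualified. A patient sampled on air at week 0 and unable to come off oxygen at Visit 6 cannot meet it.
- The interval is long enough for status to change: 12 weeks of PATENT-1 plus 12 weeks to Visit 6 = about 24 weeks.

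Some mixed pairs are therefore possible even if sites follow the protocol.

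**Step 2: effect on one patient.** Recorded change = true change on air + rise due to oxygen.

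Assumptions, not from the documents: true PaO2 change of -5 to -10 mmHg; rise of 10 to 40 mmHg.
- Smallest recorded change: -10 + 10 = 0 mmHg.
- Largest recorded change: -5 + 40 = +35 mmHg.

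Over this range a true fall is recorded as no change or as a gain.

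**Step 3: effect on the group mean.** Shift = s × r, where s is the share of patients with a Visit 6 value who were *actually sampled* on new or higher oxygen, and r is the rise due to oxygen.

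| s (assumed) | r = 10 mmHg | r = 20 mmHg | r = 40 mmHg |
|---|---|---|---|
| 2% | 0.2 | 0.4 | 0.8 |
| 5% | 0.5 | 1.0 | 2.0 |
| 10% | 1.0 | 2.0 | 4.0 |

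Example of the change in sign: with s = 5%, a true change of -10 mmHg and r = 20 mmHg, these patients should contribute 0.05 × (-10) = -0.5 mmHg to the group mean. They are recorded as contributing 0.05 × (-10 + 20) = +0.5 mmHg. The difference is the 1.0 mmHg in the table.

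**Step 4: which share applies.** s is not the share who start oxygen, because the off-oxygen default takes out everyone who can be sampled on air. If 10% started oxygen but only 2% of all patients were sampled on it, the shift at r = 40 mmHg would be 0.02 × 40 = 0.8 mmHg, not 0.10 × 40 = 4.0 mmHg.

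**The case against.** The strongest reply is that the protocol already controls this at the point of sampling. The default in 10.3 is a sample off oxygen after at least 10 minutes of rest, so starting oxygen matters only for patients who cannot come off it. Some of the patients who worsen most will also have left before Visit 6, since those needing new or changed endothelin receptor antagonist or prostacyclin therapy during titration must be withdrawn (Protocol 4.5.7). Both arguments stand. They make the upper end of the range unlikely, but they do not bring the share to zero.

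A reader might infer that new oxygen use is hidden altogether. It is not. It is documented as an event of special interest, and SAP 6.1 lists oxygen as background therapy in the concomitant medication summary. What is missing is any link between those records and the blood gas values.

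A reader might also take a change score as stated. For blood gas it is only implied by the general baseline sentence: SAP 6.4 specifies changes for laboratory and ECG data, and Protocol 6.1 for ECG, laboratory and vital signs. The point does not depend on it, because by-visit values mix oxygen conditions in the same way.

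A further tempting reading is that mixed sampling sites bias the result, since the protocol allows "Methodology: Capillary or arterial blood gas analysis" without tying a patient to one type. The documents support neither a size nor a direction for such a shift. Protocol 10.3 narrows the capillary option: "Blood gases are to be obtained from the arterial blood or from arterialized capillary blood". The PATENT-1 protocol and the CRF, which might fix or record the type, are not supplied. A new CRF item would probably come too late for Visit 6 data under a final-analysis SAP whose version 5.0 is dated 25 July 2019.

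Finally, the SAP refers to a separate TLF specifications document, which is not available here and could contain a split by oxygen. If it does, the SAP should say so.

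**Conclusion.** The point holds in a limited form. As written, SAP 6.4 combines blood gas values taken on and off oxygen although oxygen status and flow are recorded with each sample. For PaO2 and SaO2 the mixing can mask worsening. The sampling rules reduce the effect without removing it.

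The size cannot be determined from the documents. On assumed shares of 2-10% actually sampled on new or higher oxygen and an assumed rise of 10-40 mmHg, the mean PaO2 shift is about 0.2-4 mmHg, and the upper end is unlikely. A reader might go further and conclude that the table would cancel a real fall in the group mean. The documents do not support that, because they give neither the size of any fall nor the share sampled on oxygen.

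The consequence is confined to the reading of a descriptive safety table with one scheduled extension time point in the current protocol. The change is still worth making, because it needs no new data.

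**What to change.** In SAP 6.4, specify for PaO2, SaO2 and PaCO2:

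1. By-visit values, and any change from PATENT-1 week 0, presented by oxygen condition: air at both times; same flow at both times; started or increased; stopped or reduced. Pairs with a missing oxygen entry get their own row.
2. The main change summary based on same-condition pairs (the first two categories).
3. Beside it, by former PATENT-1 treatment group, the number of patients who moved from air to oxygen or to a higher flow, with their values.

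If the TLF specifications already provide such a split, carry it into the SAP text.

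The work is SAP wording and table programming on data already collected, with no change to sampling or to the CRF. The price is fewer pairs in the main summary, and the patients left out may be the sicker ones. Item 3 is therefore essential: without it, the restriction would itself remove deteriorating patients from view.
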